11. ADVERSE EVENTS AND SERIOUS ADVERSE EVENTS

The investigator is responsible for the detection and documentation of events meeting the criteria and definition of an adverse event (AE) or serious adverse event (SAE), as provided in this protocol.

All SAEs and AEs will be promptly reported from first dose of study drug administration to discontinuation of the subject from study participation. Any events occurring between screening and first dose of study drug administration will be considered as baseline, preexisting conditions.

11.1. Definition of an Adverse Event

An AE is any undesirable event that occurs to a study subject during the course of the study; that is, from the time of administration of study drugs until study ends (i.e., until the follow up visit) whether or not that event is considered related to the study drugs, or to a concomitant drug or procedure. Therefore, an AE can be absent at baseline but newly develops, or was present at baseline and worsens and includes:

- any unfavorable and unintended symptom
- physical sign
- abnormal laboratory result

• an illness

Any new clinical sign or clinical deterioration that occurs between signing the consent form and the administration of study drugs is not an AE. This information will be recorded in the medical records.

11.2. Definition of a Serious Adverse Event

A serious adverse event is any untoward medical occurrence that, at any dose:

- a. Results in death
- b. Is life-threatening

NOTE: The term 'life-threatening' in the definition of 'serious' refers to an event in which the subject was at risk of death at the time of the event. It does not refer to an event, which hypothetically might have caused death, if it were more severe.

c. Requires hospitalization or prolongation of existing hospitalization

NOTE: In general, hospitalization signifies that the subject has been detained (usually involving at least an overnight stay) at the hospital or emergency ward for observation and/or treatment that would not have been appropriate in the physician's office or out-patient setting. Complications that occur during hospitalization are AEs. If a complication prolongs hospitalization or fulfills any other serious criteria, the event is serious. When in doubt as to whether "hospitalization" occurred or was necessary, the AE should be considered serious.

Hospitalization for elective treatment of a pre-existing condition that did not worsen from baseline is not considered an AE.

d. Results in disability/incapacity

NOTE: The term disability means a substantial disruption of a person's ability to conduct normal life functions. This definition is not intended to include experiences of relatively minor medical significance such as uncomplicated headache, nausea, vomiting, diarrhea, influenza, and accidental trauma (e.g., sprained ankle) which may interfere or prevent everyday life functions but do not constitute a substantial disruption.

e. Results in a congenital anomaly/birth defect

Medical or scientific judgment should be exercised in deciding whether reporting is appropriate in other situations, such as important medical events that may not be immediately life-threatening or result in death or hospitalization but may jeopardize the subject or may require medical or surgical intervention to prevent one of the other outcomes listed in the above definition. These should also be considered serious.

Examples of such events are invasive or malignant cancers, intensive treatment in an emergency room or at home for allergic bronchospasm, blood dyscrasias, or convulsions that do not result in hospitalization, or development of drug dependency or drug abuse.

Laboratory Abnormalities and Other Abnormal Assessments as Adverse Events or Serious Adverse Events

Abnormal laboratory findings (e.g., biochemistry, hematology, urinalysis) or other abnormal assessments (e.g., BP, RR, BT, HR and ECGs) detected during the study or are present at baseline and worsen following the start of the study will be reported as AEs or SAEs.

Subjects with an adverse event will be managed clinically. This may include stopping study

drug, further investigations, treatment, referral to a specialist, etc.

11.3 Prompt Reporting of Serious Adverse Events

All SAEs should be reported promptly to medical monitor for the study within 24 hours for all SAEs to e-mail address: [contact].

If all information is not yet available then an initial report must be made within the timeframe. Further interim reports may be made if necessary or a final report when all relevant information is available.

Faculty of Tropical Medicine Ethic committee (FTM EC) will be notified within 5 official days for all SAEs.

11.4 Evaluating Adverse Events and Serious Adverse Events

11.4.1. Assessment of Intensity

All adverse events will be evaluated by the investigators and graded according to Common Terminology Criteria for Adverse Events (CTCAE) version 5.0. For lab results that are not available in Common Terminology Criteria for Adverse Events (CTCAE) version 5.0, the investigator should make a determination as to whether or not the laboratory abnormality is clinically significant. If PI believes lab abnormality is clinically significant, it should be reported as an adverse event and a grade should be identified to the best of their ability.

If an adverse event is not listed in the Common Terminology Criteria for Adverse Events (CTCAE) version 5.0, the Investigator will assess the severity using the following guidelines:

1 = Mild: asymptomatic or mild symptoms; clinical or diagnostic observations only; intervention not indicated.

2 = Moderate: minimal, local or non-invasive intervention indicated; limiting age appropriate instrumental ADL*

3 = Severe or medically significant but not immediately life-threatening; hospitalization or prolongation of hospitalization indicated; disabling; limiting selfcare ADL**

4 = Life-Threatening consequences; urgent intervention indicated

5 = Death related to AE

Activities of Daily Living (ADL)

*Age-appropriate instrumental ADL which will be defined in study SOPs.

**Age-appropriate self-care ADL which will be defined in study SOPs.

Clarification of the difference in meaning between "severe" and "serious"

The term "severe" is often used to describe the intensity (severity) of a specific event (as in mild, moderate, or severe myocardial infarction); the event itself, however, may be of relatively minor medical significance (such as severe headache). This is not the same as "serious", which is based on the outcome or criteria defined under the serious adverse event definition. An event can be considered serious without being severe if it conforms to the seriousness criteria, similarly severe events that do not conform to the criteria are not necessarily serious. Seriousness (not severity) serves as a guide for defining regulatory reporting obligations.

11.4.2. Assessment of Relatedness

The investigator is obligated to assess the relationship between study drug and the occurrence

of each AE/SAE using the following categories of relatedness:

- Definite: clear-cut temporal association, with a positive re-challenge test or laboratory confirmation.
- Probable: clear-cut temporal association, with improvement upon drug withdrawal, and not reasonably explained by the subject's known clinical state.
- Possible: less clear temporal association; other etiologies are possible. Other possible etiologies should be recorded on the CRF.
- None: no temporal association with the study drug; related to other aetiologies such as concomitant medications or conditions, or subject's known clinical state.

The investigator will provide the assessment of causality as per the instructions for completion of the AE/SAE data collection tool.

11.4.3. Action Taken

- No action taken
- Study drug is changed
- Study drug is discontinued
- No concomitant medication required
- Concomitant medication discontinued
- Concomitant medication is required
- Hospitalization required or prolonged
- Other

11.4.4. Outcome

The investigator will follow-up the AE until resolution or until no further medically relevant information can be expected. AE outcome will be classified as follows:

- Resolved
- Resolved with sequelae
- Continuing
- Death

12. DATA ANALYSIS AND STATISTICAL CONSIDERATIONS

The primary focus of statistical analysis is to verify the pharmacokinetic interactions of artemether, lumefantrine and amodiaquine in terms of $AUC_{0-\infty}$, AUC_{0-LAST} and C_{MAX} . Comparisons across groups will be made using an analysis of variance (ANOVA) of logarithmically transformed pharmacokinetic parameters (i.e. AUC_{0-LAST} , $AUC_{0-\infty}$, C_{MAX}). The criteria for assuming no interaction or equivalence when co-administered is met if confidence interval (90% CI) values for geometric mean ratios of $AUC_{0-\infty}$, AUC_{0-LAST} and C_{MAX} fall within 80% to 125% for the two groups. The point estimate of the geometric mean ratio and the residual variability from the ANOVA will be used to calculate the 90% confidence intervals around the mean.

12.1 General Considerations

All data will be summarized descriptively for the appropriate analysis sets defined below.

12.2 Analysis Sets

Safety Set

All subjects who receive study drug(s) will be included in the safety population.

Full Analysis Set

Subjects who receive the full dose of study drug without vomiting with enough samples for characterization of the concentration-time profile will be included in the pharmacokinetic analysis.

Subjects who vomit study drug or who do not have enough time points for characterization of their PK profile or with protocol violations will be replaced at the discretion of the study investigator so that the study sample size is retained for analysis.

12.3 Subject Disposition

The number of subjects recruited and receiving study drug(s) will be presented by study drug groups, as will be the number of subjects included in the various analysis populations.

Protocol violations will be listed per subject, describing the nature of the violation and specifying whether it is a major or a minor violation.

12.4 Determination of sample size

A sample size of at least 12 is recommended sample size for determining bioequivalence test (22). Therefore, we will recruit 16 healthy volunteers to ensure that we have higher power of the bioequivalence test.

12.5 Methods of statistical analysis

12.5.1 Pharmacokinetic assessments

Individual concentration-time data will be evaluated using a non-compartmental analysis approach as implemented in WinNonlin (Pharsight Corporation, California, USA). Total exposure up to the last measured concentration (AUC_{0-LAST}) will be calculated using the linear trapezoidal method for ascending concentrations and the logarithmic trapezoidal method for descending concentrations. Exposure will be extrapolated from the last observed concentration to time infinity by C_{LAST}/λ_Z for each individual subject to compute total drug exposure (AUC_{0- ∞}). The terminal elimination half-life (t_{1/2}) will be estimated by log-linear regression of the terminal phase. Maximum plasma concentration (C_{MAX}) and time to maximum concentration (T_{MAX}) will be taken directly from the observed data. Apparent volume of distribution (V_D/F) and oral clearance (CL/F) will be computed individually according to standard procedures and summarized for each treatment arm.

Pharmacokinetic parameters (i.e. AUC_{0-LAST}, AUC_{0- ∞}, C_{MAX}, T_{MAX}, CL/F, V_D/F, and t_{1/2}) will be described using means (SD or 95% CI) and medians (range) as appropriate.

12.5.2 Safety Analysis

Safety analyses will be based on the safety set. Safety and tolerability of artemether, lumefantrine and amodiaquine will be assessed by comparing the frequency (%) of adverse events and serious adverse events, with particular attention to abdominal pain, appetite perturbation and QT interval prolongation, using the Fisher's exact test. Safety data will be presented in tabular and/or graphical format and summarized descriptively. Any clinically relevant abnormalities or values of potential clinically concern will be described. Subjects will be analysed as treated.

An additional exploratory analysis evaluating independent renal markers against standard blood urea nitrogen/ creatinine levels will be conducted using appropriate statistical methods.

Adverse Events

All adverse event summaries will refer to treatment emergent adverse events, i.e. adverse

events that newly started or increased in intensity after the study drug administration. AE summaries will be generated for all AEs that occurred after study drug administration, until the end of the study.

12.6 Assessment of the relationship between pharmacokinetic parameters and ECG findings.

In addition to the results of the safety analysis, an exploratory analysis of the ECG data will be conducted. The ECG parameters will be compared with the PK properties of the drugs using appropriate statistical methods.

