4. STUDY DESIGN

This is an open-label pharmacokinetic study in 16 healthy Thai subjects. Subjects will be admitted in the inpatient ward and will be randomized to **group A** or **group B** to receive 3 drug regimens described in the following table 1. Every subject will have 1 screening and 3 admissions in the hospital.

Visit 1	Screening					
	Within 14 days					
	Group A (n = 8)	Group B (n = 8)				
Visit 2	Regimen 1	Regimen 2				
	Artemether-lumefantrine	Amodiaquine				
	on Day 0, 1, and 2	on Day 0, 1 and 2				
	Washout period: > 6 we	eeks (after day 3)				
Visit 3	Regimen 2	Regimen 1				
	Amodiaquine	Artemether-lumefantrine				

 Table 1: Study Schedule

	on Day 0, 1 and 2	on Day 0, 1 and 2		
Washout period: > 6 weeks (after day 3)				
Visit 4	Regimen 3			
	Artemether-lumefantrine + Amodiaquine on Day 0, 1 and 2			

The total duration for each subject's participation in the study is approximately 6 - 8 months depend on washout period. Study duration is approximately 12 months.

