6.1.2 Visit 2-4

16 healthy subjects who fulfill the eligibility criteria will be recruited and randomized to the study.

Procedures on each admission (Appendix 2):

Visit 2

Day -1 (admission)

- Physical Examination and symptoms questionnaire assessment
- Chemistry, Hematology, FBS and urinalysis assessment
- 24-hour urine for creatinine clearance test
- Genetic sample collection (Genetic sample can be collected at any of the subsequent days or visits, if it is missed today)
- Vital signs will be checked every 4 hours.
- ECG monitoring according to table 2
- Holter monitoring (~30 mins baseline recording)
- Urine pregnancy test (if applicable)

Day 0-3 (admission)

- Daily physical examination and symptoms questionnaire assessment
- Vital signs will be checked before and every 4 hours after first dose.
- ECG monitoring according to table 2
- Continuous Holter monitoring during admission.
- Pharmacokinetic samples will be collected according to table 2
- Study drug administration (Artemether-lumefantrine OR Amodiaquine) will be given according to table 1.
- 24-hour urine for creatinine clearance test (Day 2)
- Chemistry, Hematology, FBS and urinalysis assessment before discharge

Day 4 (+1) (follow up)

• Physical Examination, vital signs and symptoms questionnaire assessment

- Pharmacokinetic sample collection
- ECG

Day 7 (+/-2d) (follow up)

- Physical Examination, vital signs and symptoms questionnaire assessment
- Chemistry, Hematology and urinalysis assessment
- Pharmacokinetic sample collection
- ECG
- Holter monitoring (~ 30 mins)

Day 14 (+/-2d) (follow up)

- Physical Examination, vital signs and symptoms questionnaire assessment
- Chemistry, Hematology and urinalysis assessment
- Urine pregnancy test (if applicable)
- Pharmacokinetic sample collection
- ECG

Day 21 (+/-2d) (follow up)

- Physical Examination, vital signs and symptoms questionnaire assessment
- Chemistry, Hematology and urinalysis assessment
- ECG

Day 28 (+/-2d) (follow up)

- Physical Examination, vital signs and symptoms questionnaire assessment
- Chemistry, Hematology and urinalysis assessment
- Urine pregnancy test (if applicable)
- Pharmacokinetic sample collection
- ECG
- Holter monitoring (~ 30 mins)

Day 35 (+/-2d) (follow up) (for Amodiaquine only)

- Physical Examination, vital signs and symptoms questionnaire assessment
- Chemistry, Hematology and urinalysis assessment
- ECG

Day 42 (+/-2d) (follow up) (for Amodiaquine only)

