- Chemistry, Hematology and urinalysis assessment
- Urine pregnancy test (if applicable)
- Pharmacokinetic sample collection
- ECG

Visit 4

Day -1 (admission)

- Physical Examination and symptoms questionnaire assessment
- Chemistry, Hematology, FBS and urinalysis assessment
- 24-hour urine for creatinine clearance test
- Vital signs will be checked every 4 hours.
- ECG monitoring according to table 2
- Holter monitoring (~30 mins baseline recording)
- Urine pregnancy test (if applicable)

Day 0-3 (admission)

- Daily physical examination and symptoms questionnaire assessment
- Vital signs will be checked before and every 4 hours after first dose.
- ECG monitoring according to table 2
- Continuous Holter monitoring during admission.
- Pharmacokinetic samples will be collected according to table 2
- Study drug administration (Artemether-lumefantrine AND Amodiaquine) will be given according to table 1.
- 24-hour urine for creatinine clearance test (Day 2)
- Chemistry, Hematology, FBS and urinalysis assessment before discharge

Day 4 (+1) (follow up)

- Physical Examination, vital signs and symptoms questionnaire assessment
- Pharmacokinetic sample collection
- ECG

Day 7 (+/-2d) (follow up)

- Physical Examination, vital sign and symptoms questionnaire assessment
- Chemistry, Hematology and urinalysis assessment
- Pharmacokinetic sample collection
- ECG
- Holter monitoring (~ 30 mins)

Day 14 (+/-2d) (follow up)

- Physical Examination, vital signs and symptoms questionnaire assessment
- Chemistry, Hematology and urinalysis assessment
- Urine pregnancy test (if applicable)
- Pharmacokinetic sample collection
- ECG

Day 21 (+/-2d) (follow up)

- Physical Examination, vital signs and symptoms questionnaire assessment
- Chemistry, Hematology and urinalysis assessment
- ECG

Day 28 (+/-2d) (follow up)

- Physical Examination, vital signs and symptoms questionnaire assessment
- Chemistry, Hematology and urinalysis assessment
- Urine pregnancy test_(if applicable)
- Pharmacokinetic sample collection

- ECG
- Holter monitoring (~ 30 mins)

Day 35 (+/-2d) (follow up)

- Physical Examination, vital signs and symptoms questionnaire assessment
- Chemistry, Hematology and urinalysis assessment
- ECG

Day 42 (+/-2d) (follow up)

- Physical Examination, vital signs and symptoms questionnaire assessment
- Chemistry, Hematology and urinalysis assessment
- Urine pregnancy test (if applicable)
- Pharmacokinetic sample collection
- ECG

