6.4. Pharmacokinetics

Blood for pharmacokinetic assessments may be obtained by individual needle stick or IV

cannula. If a cannula is used for collection of the whole blood samples, the cannula will be inserted into an arm vein within sufficient time before dosing and may be kept patent using a dilute heparin solution as a flush. An initial volume of approximately 1.0 mL of blood will be collected and discarded prior to collection of each whole blood sample to ensure that the saline or heparin solution does not artificially dilute the samples. If PK samples are collected via individual needle sticks rather than through a cannula, then no extra blood needs to be collected and discarded prior to the collection of the sample.

Each blood sample will be labeled with subject's number, schedule date and time, collection date and time. The actual time of each blood sample will be recorded on the case report form (CRF).

Regimen	Blood sampling	ECG measurements
Regimen 1: Artemether- lumefantrine (AL) Dosing: 0h, 8h, 24 h, 36 h, 48 h, 60 h	 Day 0: Hr. 0 (pre-dose), 0.25, 0.5, 1, 2, 3, 4, 6, 8 (pre-dose), 10, 12, 14 Day 1: Hr. 24 (pre-dose), 26, 28, 30, 36 (pre-dose), 38, 40, 42 Day 2: Hr. 48 (pre-dose), 48.25, 48.5, 49, 50, 51, 52, 54, 56, 60 (pre-dose), 61, 62, 64, 66 Day 3: Hr. 72 Day 4, Day 7, Day 14, Day 28 	Day -1: Hr. 0, 1, 2, 4, 6, 8, 10, 12, 14 Day 0: Hr. 0 (pre-dose), 1, 2, 4, 6, 8 (pre-dose), 10, 12, 14 Day 1: Hr. 24 (pre-dose), 26, 28, 30, 36 (pre-dose), 38, 40, 42 Day 2: Hr. 48 (pre-dose), 49, 50, 52, 54, 60 (pre-dose), 61, 62, 64, 66 Day 3: Hr. 72 Day 4, Day 7, Day 14, Day 21, Day 28
Regimen 2: Amodiaquine (AQ) Dosing: 0h, 8h, 24 h, 36 h, 48 h, 60 h	Day 0: Hr. 0 (pre-dose), 0.25, 0.5, 1, 2, 3, 4, 6, 8 (pre-dose), 10, 12, 14 Day 1: Hr. 24 (pre-dose), 26, 28, 30, 36 (pre-dose), 38, 40, 42 Day 2: Hr. 48 (pre-dose), 48.25, 48.5, 49, 50, 51, 52, 54, 56, 60 (pre-dose), 61, 62, 64, 66 Day 3: Hr. 72 Day 4, Day 7, Day 14, Day 28, Day 42	Day -1: Hr. 0, 1, 2, 4, 6, 8, 10, 12, 14 Day 0: Hr. 0 (pre-dose), 1, 2, 4, 6, 8 (pre-dose), 10, 12, 14 Day 1: Hr. 24 (pre-dose), 26, 28, 30, 36 (pre-dose), 38, 40, 42 Day 2: Hr. 48 (pre-dose), 49, 50, 52, 54, 60 (pre-dose), 61, 62, 64, 66 Day 3: Hr. 72 Day 4, Day 7, Day 14, Day 21, Day 28, Day 35, Day 42

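### By regimen, AL+AQ and AL adverse events would be compared over unequal safety surveillance (Day 42 versus Day 28), with no common window and no rule for late events

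*Protocol*

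**What the plan says.** **Visit schedule.** In Protocol 6.1.2, for Visits 2 and 3, the last two follow-up visits are restricted: "Day 35 (+/-2d) (follow up) (for Amodiaquine only" and "Day 42 (+/-2d) (follow up) (for Amodiaquine only". After AL alone the last scheduled visit is therefore Day 28. Protocol Table 2 (section 6.4) agrees, giving the follow-up ECGs after AL as "Day 4, Day 7, Day 14, Day 21, Day 28". At Visit 4, when every subject takes AL+AQ, the corresponding entry reads "Day 42 (+/-2d) (follow up" with no such restriction. The Day 35 and Day 42 visits each include an examination, the symptom questionnaire, vital signs, chemistry, haematology, urinalysis and an ECG.

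**What counts as an event.** Protocol 11.2 covers abnormal laboratory, vital-sign and ECG findings. Those "detected during the study or are present at baseline and worsen following the start of the study will be reported as AEs or SAEs".

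**Collection and analysis.** Protocol 11 has events reported from the first dose until the subject leaves the study. Protocol 12.5.2 plans "comparing the frequency (%) of adverse events and serious adverse events" by Fisher's exact test, as treated, and adds that "AE summaries will be generated for all AEs that occurred after study drug administration, until the end of the study". It names no regimen contrast, sets no window per regimen and makes no exposure adjustment. The gap between regimens is set in Protocol 4: "Washout period: > 6 weeks (after day 3".

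**SAP.** Section 3.5.3 reports adverse events by randomised sequence (AL, AQ, AL+AQ versus AQ, AL, AL+AQ), not by regimen.

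**The concern.** Tolerability of the co-administered drugs is a secondary objective (Protocol 2.2). The contrast that shows what amodiaquine adds is AL+AQ versus AL, and it is the one by-regimen contrast with the combination in which scheduled follow-up differs. Two further full visits give the combination two further chances to record a symptom, a chance laboratory abnormality or an ECG finding. A crude percentage cannot separate those from a drug effect.

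No document says where the AL observation period ends, or which regimen owns an event between the last AL visit and the next dose. The size and direction of the imbalance therefore depend on a choice that would be made after the data are seen, in an open-label study of 16 subjects where one or two extra cases are visible in the table.

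**Working it through.** **1. Confirm the schedule against the plan's own totals.**
- Blood volume (Protocol Appendix 4), as Day -1 panel + discharge panel + follow-up panels + inpatient PK + follow-up PK:
  - AL to Day 28: 9 + 9 + 4×7 + 35 + 4×1 = 85 mL
  - AQ to Day 42: 9 + 9 + 6×7 + 35 + 5×1 = 100 mL
  - AL+AQ to Day 42: 9 + 9 + 6×7 + 70 + 5×2 = 140 mL
  - Total with screening and the genetic sample: 10 + 85 + 100 + 140 + 10 = 345 mL
- Compensation (Protocol 13.5): 500 × (1 + 5 + 7 + 7) + 3 × 6,000 = 28,000 baht.

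All match the stated figures, so the schedule is intended: 5 follow-up visits after AL, and 7 after AQ and after AL+AQ.

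**2. Count the surveillance after the first dose.**

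| | AL | AL+AQ | Ratio |
|---|---|---|---|
| Last scheduled visit | Day 28 | Day 42 | 1.5 |
| Laboratory panels (Days 3, 7, 14, 21, 28; plus 35, 42) | 5 | 7 | 1.4 |
| ECG time points (8 + 8 + 10 + 1 inpatient, plus 5 or 7) | 32 | 34 | 1.06 |

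**3. Reading A: AL events stop at the last scheduled visit.** The documents give no background rate, so I assume that a share p28 of subjects has at least one event by Day 28, with constant hazard and no added drug effect. Then p42 = 1 − (1 − p28)^(42/28).

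| p28 (AL) | p42 (AL+AQ) | Extra subjects of 16 |
|---|---|---|
| 5% | 7.4% | 0.4 |
| 10% | 14.6% | 0.7 |
| 20% | 28.4% | 1.4 |
| 30% | 41.4% | 1.8 |
| 50% | 64.6% | 2.3 |
| 70% | 83.6% | 2.2 |

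Over these rates, the chance that a two-sided 5% Fisher test (16 versus 16) wrongly shows the combination as worse is 0.2% to 7.1%. With equal windows it is 0.04% to 1.0%. These figures treat the two samples as independent. The same subjects take both regimens, so they are approximate.

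For laboratory findings alone, assume independent panels with chance q of a reportable abnormality: 1 − (1 − q)^5 versus 1 − (1 − q)^7. This gives 22.6% versus 30.2% at q = 5%, and 41.0% versus 52.2% at q = 10%.

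**4. Reading A with mostly acute events.** If 30% to 70% of subjects have an early event on either regimen, and background by Day 28 is 5% to 20%, the excess on AL+AQ is 0.7 to 5.9 percentage points (0.1 to 0.9 subjects of 16).

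**5. Reading B: AL events are counted to the next dose.** The washout exceeds 42 days after Day 3, so the next dose falls after about Day 45. With p45 = 1 − (1 − p28)^(45/28), AL versus AL+AQ becomes 15.6% versus 14.6% (p28 = 10%), 43.6% versus 41.4% (30%) and 67.2% versus 64.6% (50%). The next admission's Day -1 work-up adds one laboratory panel and nine ECG time points to AL: 6 versus 7 panels, and 32 + 9 = 41 versus 34 ECG time points. Chance laboratory findings are then 26.5% versus 30.2% (q = 5%) or 46.9% versus 52.2% (q = 10%).

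**6. The SAP's comparison.** Both sequences contain AL, AQ and AL+AQ once each, so planned follow-up per subject is equal and this bias is zero there. The combination also appears on both sides, so its effect is not estimated.

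**The case against.** A reader might infer that the combination is bound to look worse. The documents do not support that, for three reasons.

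- **Capture does not stop at Day 28.** Reporting is continuous under Protocol 11. AL is never the last regimen, so every continuing subject has a full Day -1 work-up at about Day 45 or later, before the next dose. Only events before the first dose of study drug are set aside as baseline, so new Day -1 findings are reportable. Nothing comparable follows AL+AQ. Attributed to AL, these findings reverse the time and ECG imbalance and narrow the laboratory one. This stands, and it removes any claim about a fixed direction.
- **The contrast is not named.** Protocol 12.5.2 does not specify AL+AQ versus AL, and the SAP compares sequences. This stands as a description. It is not a defence, because a sequence comparison cannot meet the tolerability objective, while the as-treated wording and Protocol 12.3 (disposition by study drug groups) point to a regimen comparison.
- **The effect is modest.** The rates above are assumptions. Dosing ends at 60 h, and the events singled out in Protocol 12.5.2 (abdominal pain, appetite, QT) may well be early. ECG counts are nearly equal, and false significance stays at or below about 7%. This stands too, and limits the point to a recommended change.

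Longer follow-up after amodiaquine also fits the half-lives in Protocol 1 (desethylamodiaquine 9 to 31 days, lumefantrine 3 to 6 days). The visit schedule is not at fault. The missing analysis window is.

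**Conclusion.** The point holds in a limited form. By regimen, scheduled safety surveillance after AL and after AL+AQ is unequal, and neither document sets a common window or says which regimen owns late events. If AL is cut at its last visit, the combination gains about 0.4 to 2.3 subjects of 16 with no drug effect, or 0.1 to 0.9 if most events are acute. If AL runs to the next dose, the time and ECG imbalance disappears or slightly reverses, leaving 6 versus 7 laboratory panels. These sizes rest on assumed rates, constant background hazard and independent panels. The schedule counts come from the documents.

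Scheduled follow-up for AL+AQ versus AQ is equal to Day 42. The SAP's sequence comparison is free of this bias but does not address the tolerability of the combination. The matter should be settled before analysis. It does not threaten the primary pharmacokinetic objective.

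**What to change.** In Protocol 12.5.2 and SAP 3.5.3:

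1. Report adverse event, laboratory and ECG outcomes by regimen (AL, AQ, AL+AQ).
2. Compare AL+AQ with AL from first dose to Day 28, plus the visit window. Compare AL+AQ with AQ over Day 0 to Day 42.
3. List Day 29 to 42 events separately as late follow-up.
4. Assign events between the last visit and the next dose, and new Day -1 findings, to the preceding regimen, and list them outside the common window.

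With a common window, the expected difference under no drug effect is zero in either direction.

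The cost is wording in both documents and a move of the SAP safety tables from sequence to regimen. Visits, sampling and data collection are unchanged. The one loss is that events after Day 28 leave the AL+AQ versus AL contrast. They stay in the listing and in the comparison with AQ, which matters because desethylamodiaquine is eliminated slowly.
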